A (prospective/pilot) study evaluating the effect of cataract surgery on the daily activity levels of elderly patients.

[name], O.D.
[name].
[name], O.D., F.A.A.O.
[name].
[name], O.D., M.D.
[name], O.D.

Bennett and Bloom Eye Centers
[name]
[name]
[name]
[contact]
[contact]

Title: A (prospective/pilot) study evaluating the effect of cataract surgery on the daily activity levels of elderly patients.

Purpose: To evaluate the effect of bilateral cataract surgery with intraocular lens implantation on the daily activity levels of elderly patients.

Objective: The primary endpoint is the comparison of baseline activity levels to post-operative week two activity levels in patients undergoing bilateral cataract surgery using the ActiGraph GT9X wrist monitor.

Background: Cataract formation is a natural aging process that can be influenced by environmental factors such as exposure to ultra violet light and diet (1). Additionally, metabolic disorders, such as diabetes can lead to an earlier development of cataracts (2).

As cataracts develop, a patient's vision can be affected (3). Reduced vision can limit activities of daily living and may even reduce a patient's mobility (4). When this occurs, cataract surgery should be considered to help restore a patient's vision.

With the obesity and diabetic epidemic, proper diet and exercise is a major health initiative to control these diseases (5). If a patient's mobility is reduced as a result of poor vision - their ability to achieve adequate daily physical activity may also be effected (6). It is thought that improvement in vision may increase their activity levels and help combat these health issues.

This study will investigate the activity level of patients before and after undergoing cataract surgery to determine how improved vision quality from removal of the natural lens inside the eye and replacement with an artificial intraocular lens effects their activity level.

Study population: Adult patients undergoing bilateral cataract surgery and adult patients who have cataracts but are not undergoing cataract. Consecutive patients based on the inclusion criteria will be selected for the study.

Study design: Prospective

Masking: None

Randomization: None

Method: Consecutive patients who meet the inclusion criteria will be asked to participate in the study. Patients scheduled for bilateral cataract surgery will be asked to wear a wrist accelerometer (Actigraph Inc, Pensacola, FL) 10 days prior to their cataract surgery in their first eye to determine their baseline activity level (7). The device is the size of a wrist watch and will have minimal burden to patients. Each monitor will be fitted

on the wrist and worn for 24 hours a day, but can be quickly removed for medical procedures, patient care, or hygiene needs. Data, such as steps per day, total movements per day, minutes being sedentary and minutes moving at various intensities (e.g. light, moderate and vigorous), will be collected and analyzed to determine a patient's overall general physical activity level. Set standards and cut offs will be used to correlate wrist accelerometry to physical activity and this has been studied previously. The patient will then undergo bilateral cataract surgery, having each eye done a week or two apart and both eyes set for distance. Cataract surgery will be performed in its usual manner using the standard post-operative care. Patients will then be asked to wear the wrist accelerometer again for 10 days following their surgery to measure their post-operative physical activity level. Wrist monitors can be mailed to and from patients using prepaid envelopes. The pre and post-operative data will be analyzed to determine cataract surgery's effect on pre and post-operative activity levels.

To control for placebo effects, a control group of patients who have visually significant cataracts but are not interested in cataract surgery at this time will also be asked to participate in the study. They will wear their wrist monitor for 10 days to collect base line data and then wear the wrist monitor again 14 days later for another 10 days.

Sample size: 30 patients will be enrolled in the study

Length of study: 12 months

Inclusion Criteria:

- Patients undergoing bilateral cataract extraction by phacoemulsification with intraocular lens implantation and a planned bilateral distance vision target or patients with bilateral cataracts who are not having cataract surgery
- Patients aged 60 years old or older
- Best corrected visual acuity worse than 20/20 in each eye (meaning 20/25 or worse)
- Non-comanged patients

Exclusion criteria:

- Greater than 0.76 D pre-operative corneal cylinder, if having cataract surgery without a planned astigmatism correction (i.e. Limbal relaxing incision or Toric intraocular lens)
- Planned implantation of a multifocal intraocular lens
- Visual field defect which may reduce mobility
- Wheel chair bound patients
- Reduced vision from an ocular disease other than cataracts
- Patients with significant dementia who are not able to fully comprehend the informed consent

Examinations:

Cataract surgery group

- Baseline/pre-operative exam
- Cataract surgery first eye
- Post-operative exam one, 1-3 days after cataract surgery first eye
- Cataract surgery second eye
- Post-operative exam two, 1-3 days after cataract surgery second eye
- Post-operative exam three, 14-21 days after cataract surgery second eye

Cataract non-surgery group

- Baseline/pre-operative exam

Baseline exam/Pre-Operative exam:

- Ocular history
- Medical history
- Family history
- Social history
- Blood pressure
- Vitals (Pulse, blood pressure)
- Anthropometrics (Height, weight, body mass index)
- Pupils
- Extraocular Muscles
- Confrontation fields
- Best correct visual acuity
- Manifest refraction
- Keratometry
- Intraocular Pressure
- Slit lamp exam
- Dilated fundus exam
- Other various health-related questionnaires (e.g., CHAMPS activity questionnaire)

Post-Operative Exam One

- Visual acuity first eye
- Intraocular Pressure first eye
- Slit Lamp Exam first eye

Post-Operative Exam Two

- Visual acuity both eyes
- Intraocular Pressure both eyes
- Slit Lamp Exam both eyes

Post-Operative Exam Three

- Best Corrected Visual Acuity both eyes
- Manifest refraction

- Intraocular Pressure both eyes
- Slit Lamp Exam both eyes
- Dilated fundus exam both eyes
- Health-related questionnaires (follow-up)

Risk/Safety Information:

A. Potential risks:

The risks of wearing the mobility monitor are similar to wearing a wristwatch. If applied and adjusted properly, there is minimal risk of skin breakdown or sores.

The risk of cataract surgery is not increased in this study and the routine cataract surgery procedure is not considered part of this study. With any surgical procedure there are risks and the standard risk of cataract surgery include infection, inflammation, loss of vision, increased intraocular pressure that may lead to glaucoma, bleeding, retinal detachment, damage to the cornea and corneal edema (swelling of the tissue in the front part of your eye), damage to the iris (the colored part of your eye), cystoid macular edema (swelling of the tissue in the back of your eye), or death, although this would be an extremely rare complication. You may need additional surgery to replace or reposition the intraocular lens or to treat any other ocular complications.

B. Potential benefits to be gained by the subject:

Potential increased physical activity and improvement in vision and activities of daily living would be a benefit to patients undergoing cataract surgery. Patients in both groups may benefit by knowing they are potentially contributing to the increasing body of scientific knowledge.

C. Potential benefits or information which may accrue to science or society in general, as a result of this work.

Evidence to determine if cataract surgery increases physical activity may help patients increase their exercise and combat obesity, diabetes, and heart disease.

D. Potential risks to subjects are reasonable in relation to anticipated benefits.

Cataract surgery is one of the most common surgeries performed in the United States and the risk of serious vision loss is low. Patients undergoing cataract surgery can expect to have an improvement in their vision. The risks from wearing a wrist watch size activity monitor are extremely low and pose a minimum burden to patients.

Monitoring/Reporting Adverse Events:

Adverse events will be monitored by the primary and sub-investigators at each study site. Adverse events will be documented and properly reported to the study IRB when

indicated. All investigators will have direct phone access to the lead investigator 24/7 for emergency situations. Data on adverse events will be reported and checked monthly by the primary investigator at each site as well as the lead investigator to ensure that there is no increased risk to the study subjects.

Study Oversight: This study will be prematurely terminated if the procedure or medications are found to have a risk profile that outweighs their benefit for the study. This determination will be made by the lead investigator/sponsor in consultation with the primary investigators and IRB. The study will provide direct access to the study data for the purposes of monitoring, auditing, IRB review, and regulatory inspection.

Data Management and Safety Monitoring:

A. Who will be responsible for the data and safety monitoring?

The lead investigator and the primary investigator at the research site will be responsible for data safety monitoring. The investigators are not independent from the study.

B. What will be monitored?

Only subjects who meet the study eligibility criteria will be enrolled in this study. Additionally, the informed consent process will be conducted appropriately and informed consent will be obtained prior to any study procedure being performed. Data will be collected and analyzed by the guidelines set forth by the study protocol and adverse events will be reviewed promptly and reported as required to the IRB. HIPPA will be complied with at all times throughout the study and all patients will be assigned unique identifying numbers. The number of study dropouts will also be closely monitored.

C. What are the procedures for analysis and interpretation of data, the actions to be taken upon specific events or endpoints, the procedures for communication from the data monitor to the IRB and site, and other reporting mechanisms?

The Primary and sub-investigator(s) at the testing site will be responsible for the collection and storage of all study data. Data will be stored in a password protected cloud storage site and organized into an excel spreadsheet. The identity of each patient will be protected using a unique identifying number. A second spreadsheet will match that unique number with that patient's name, and will be stored separately under password protection. The lead and principal investigators will evaluate the current data collection monthly to make sure it is in order and the study performance is progressing without incident. After study completion, all collected data will be analyzed by appropriate statistical tools.

D. What is the frequency of monitoring?

Study data will be grossly monitored on a monthly basis to ensure that the study is

performing smoothly and that all data is being collected in accordance with the set study protocol.

E. What information will be reported to the IRB?

All necessary data will be reported to the IRB in a prompt manner including but not limited to the frequency and dates of data monitoring, a cumulative summary of adverse events, an assessment of new research that could impact the safety of the subjects, a summary of privacy and data confidentiality breaches, and any changes to the procedures risk-benefit ratio.

Informed consent: The protocol, informed consent document, and relevant supporting information will be submitted to the IRB for review and will be approved before the study is initiated. In addition, any subject recruitment materials will be approved by the IRB prior to being used. This study will be conducted in accordance with the ethical principles that have their origin in the Declaration of Helsinki and that are consistent with Good Clinical Practice and applicable regulatory requirements. The study must be conducted in accordance with the regulations of the United States Food and Drug Administration (FDA) as described in 21 CFR 50 and 56 [add 312 for IND studies or 812 for device studies], applicable laws and the IRB requirements. Any change to the protocol will be submitted to the IRB for review and approval before implementation. A protocol change intended to eliminate an apparent immediate hazard to subjects will be implemented immediately provided the FDA and the reviewing IRB are notified within 10 working days.

It is the responsibility of the investigator to provide each subject with full and adequate verbal and written information using the IRB approved informed consent document, including the objective and procedures of the study and the possible risks involved before inclusion in the study. Informed consent must be obtained prior to performing any study-related procedures, including screening and changes in medications including any washout of medications. A copy of the signed informed consent must be given to the study subject.

1. When and where will consent take place?

Informed consent will take place at the eye care facility during normal business hours in either a private office or exam room. If a patient meets the eligibility requirements as determined by the primary investigator or sub-investigator they will inform the patient of the study and the risks/benefits/alternatives of the procedure in English. The subject will be given adequate time to weigh their options and the risk/benefits/alternatives of the study. If after adequate time is given, and all questions are answered, the subject wishing to participate will sign the informed consent documentation and they will be enrolled in the study. All primary and sub-investigators for the study will be required to pass the National Institute of Health Protecting Human Research Participants certification.

2. How will the subject's privacy be protected during the consent process?

Each testing site will comply with HIPAA guidelines at all times. Informed consent will be performed during normal business hours at the eye care facility. The informed consent will be conducted in a private office or exam room.

Subject Payment and Costs: Subjects will not be paid for participating in this study. Subjects taking part in this study may incur added costs to themselves or their insurance company. The subject or their insurance company will be responsible for the following costs: All standard of care procedures, exams, and testing including cataract surgery and implantation of an intraocular lens. Patients may choose an upgrade cataract surgery package if they wish to reduce their dependence on glasses following cataract surgery.

Confidentiality: Efforts will be made to keep each subject's personal information confidential. All electronic data will be password protected, all paper records will be kept in private locked rooms, and patients in the study will be identified by unique ID numbers. However, we cannot guarantee absolute confidentiality. Personal information may be disclosed if required by law. Subject's identity will be held in confidence in reports in which the study may be published and databases in which results may be stored.

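### The primary comparison uses only the surgery patients' before/after change and leaves out the control group enrolled to guard against placebo effects

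*Protocol*

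**What the plan says.** The Objective fixes the primary comparison: "The primary endpoint is the comparison of baseline activity levels to post-operative week two activity levels in patients undergoing bilateral cataract surgery". The Background frames the aim the same way: "This study will investigate the activity level of patients before and after undergoing cataract surgery to determine how improved vision quality". In the Method section, the paragraph on the surgery patients ends with the only sentence that says how the effect will be judged: "The pre and post-operative data will be analyzed to determine cataract surgery's effect on pre and post-operative activity levels".

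The next Method paragraph brings in the second group: "To control for placebo effects, a control group of patients who have visually significant cataracts but are not interested in cataract surgery". These patients wear the monitor for a first 10-day period and later for a second one of the same length. The design section states "Randomization: None", and there is no masking. Thirty patients are planned in total, with no split between the groups. The only other statement on analysis is in Data Management and Safety Monitoring, item C. It says that all the data will be analysed with suitable tools and names no comparison.

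Three statements bear on timing. Surgery patients "wear the wrist accelerometer again for 10 days following their surgery to measure their post-operative physical activity level", with the operations described as "having each eye done a week or two apart". Controls "wear the wrist monitor again 14 days later for another 10 days".

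**The concern.** The question is causal: what does surgery do to activity? A before/after change in operated patients contains the effect of surgery plus anything else that moves activity between the two wear periods. Candidates are a response to being monitored a second time and season, although season may partly cancel if enrolment spreads over the 12 months. The control group is measured twice and could be used to estimate that common part, but the stated primary comparison does not use it. Non-surgery patients have no post-operative data, so the analysis sentence in the Method does not cover them either.

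At stake is the meaning of the main result. As written it answers whether activity changed after surgery. It does not answer whether activity changed more than in comparable patients who were not operated on. In a pilot, the practical harm is a biased effect estimate carried forward.

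**Working it through.** **1. Is the group comparison stated anywhere?** The Objective names surgery patients only. The Method's analysis sentence refers to pre- and post-operative data. The control paragraph gives a reason for the group and a wear schedule, but no comparison. Item C of Data Management names no contrast. So the primary comparison is fixed without the control group.

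**2. What does a shared drift do to the stated comparison?** The protocol names no test and gives no figure to reproduce here, so every input below is assumed: 15 surgery patients, a paired t test at two-sided 5%, and no true surgery effect. Drift *d* is in units of the between-patient SD of activity, and *r* is the correlation between baseline and follow-up.

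The SD of an individual change is √(2(1−r)). The noncentrality is d·√n / √(2(1−r)), with n−1 = 14 degrees of freedom. For example, at d = 0.2 and r = 0.8 it is 0.2 × 3.873 / 0.632 = 1.22.

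| Shared drift | r = 0.5 | r = 0.8 | r = 0.9 |
|---|---|---|---|
| 0.05 SD | 5.4% | 5.9% | 6.9% |
| 0.1 SD | 6.5% | 8.8% | 12.7% |
| 0.2 SD | 11.2% | 20.8% | 36.5% |
| 0.2 SD, n = 20 | 13.6% | 26.9% | 47.6% |

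The bias in the estimate equals the drift itself, whatever the group split.

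**3. What does the difference in change do?** A drift common to both groups cancels by subtraction. Simulation (20,000 runs per case, drift 0.2 SD, groups of 15/15 and 20/10, stable group differences of 0, 0.5 and 0.8 SD, and the three values of r) gave bias within 0.005 SD and rejection in 4.6–5.3% of runs. Identical drift was an input, so this confirms the algebra. It does not show that the real groups drift alike.

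**4. What does it cost in precision?** The SE of the difference in change is √(2(1−r)(1/n₁+1/n₂)). The SE of the within-group change is √(2(1−r)/n₁). At r = 0.8 and 15/15 these are √(0.4 × 0.1333) = 0.231 and √(0.4/15) = 0.163. The 95% half-widths are 2.048 × 0.231 = 0.47 and 2.145 × 0.163 = 0.35.

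| 95% half-width (SD) | r = 0.5 | r = 0.8 | r = 0.9 |
|---|---|---|---|
| Within surgery group, n = 15 | 0.55 | 0.35 | 0.25 |
| Difference in change, 15/15 | 0.75 | 0.47 | 0.33 |
| Difference in change, 20/10 | 0.79 | 0.50 | 0.35 |

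**5. Change score or baseline-adjusted ANCOVA?** Let the groups differ at baseline by D. If that difference is stable, ANCOVA is biased by about (1−r)D. With D = 0.5 and 15/15 the bias is 0.25, 0.10 and 0.05 SD at r = 0.5, 0.8 and 0.9, and the rejection rates are 11.8%, 7.3% and 5.9%. If the gap is transient, shrinking to rD at follow-up, the difference in change is biased by the same amount in the other direction (−0.25, −0.10, −0.05 SD) and rejects in 10.1%, 7.1% and 5.8%.

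**6. Are the wear intervals comparable?** Take the first wear in surgery patients to end at first-eye surgery, with the second eye 7–14 days later.

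- Re-wear from second-eye surgery: a gap of 7–14 days.
- Re-wear from the start of the second post-operative week: 7+7 to 14+7 = 14–21 days.
- Re-wear from the two-week point (when the window for exam three opens): 7+14 to 14+14 = 21–28 days.
- Controls: 14 days if counted from the end of the first wear, or 14−10 = 4 days if counted from its start.

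**The case against.** The strongest reply is that the intent to compare is plain from the stated reason for the control group and from its parallel schedule, and that the method of comparison belongs in an SAP that may exist. On this view the Method's analysis sentence simply closes the surgery paragraph and excludes nothing. This is fair as regards the model. It does not rescue the Objective, which fixes the primary contrast in this document and leaves the control group out of it. An SAP could add a group comparison, but the protocol's primary result would still be surgery patients only.

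A second reply is that the error rates rest on assumed drift. That stands: at 0.05 SD the inflation is slight, and nothing in the protocol supports one value over another. The figures show direction and sensitivity, not an expected size.

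A third is that the control group is a weak remedy. Its members are self-selected, unmasked and have no sham procedure, and an uneven split would leave little information. At 25/5 and r = 0.8 the half-width is 2.048 × √(0.4 × 0.24) = 0.63 SD. This also stands, and it is why an estimate with an interval is asked for and not a confirmatory test. The choice between change score and ANCOVA cannot be settled from the protocol either, so both should be shown.

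Finally, the timing question is separate from the choice of contrast, and the 4-day reading for controls is the less natural one. It matters here because changes over unlike intervals are harder to compare.

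**Conclusion.** The point holds and should be fixed. The protocol's primary comparison omits the group enrolled to serve as its control, so any change common to both groups would be counted as an effect of surgery. This follows from the text and does not depend on the group split.

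The size is not known. On the assumed inputs (15 surgery patients, paired test, no surgery effect), false-positive rates run from near the nominal 5% for very small drift to 37% for a drift of 0.2 SD at r = 0.9. The between-group comparison removes shared change only, and only if both groups would have drifted alike. Confounding and part of any placebo response would remain.

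**What to change.** - **Objective:** state the primary comparison as the difference between groups (surgery minus non-surgery) in change from baseline activity, reported as an estimate with a 95% confidence interval. Keep the within-surgery-group change as secondary.
- **Method, analysis sentence:** bring the control group's two wear periods into the statement of how surgery's effect is judged.
- **Sensitivity analysis:** show baseline-adjusted ANCOVA, with age and baseline best corrected acuity as covariates, beside the primary estimate. Each method is biased under the other's assumption about the baseline gap.
- **Limits:** say that the comparison removes shared change, and that self-selection and the lack of masking or a sham procedure leave confounding and part of any placebo effect in place.
- **Wear windows:** reconcile the Objective's second-week wording with the two Method statements. Give the starting point of each window, so that the interval between wear periods is comparable in the two groups.

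The cost is rewording, with no added patients or visits. The price is precision: at an assumed 15/15 and r = 0.8, the half-width rises from 0.35 to 0.47 SD.

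### The primary endpoint is post-operative week two, but the 10-day post-operative wear has no start day and no anchoring eye, so how much of week two is recorded is not fixed

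*Protocol*

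**What the plan says.** - Protocol, Objective: "The primary endpoint is the comparison of baseline activity levels to post-operative week two activity levels in patients undergoing bilateral cataract surgery". The days that make up week two are not defined.
- Protocol, Method, baseline: the surgery group wears the monitor "10 days prior to their cataract surgery in their first eye to determine their baseline activity level".
- Protocol, Method, after surgery: "Patients will then be asked to wear the wrist accelerometer again for 10 days following their surgery to measure their post-operative physical activity level". The eyes are operated on one to two weeks apart, and the sentence does not say which operation starts the count.
- Protocol, Method, analysis: "The pre and post-operative data will be analyzed to determine" the effect of surgery. The post-operative value is not limited to particular days.
- Protocol, Method, controls: the second 10-day wear comes after a 14-day interval. This is the only stated timing for a second wear, and it is not applied to the surgery group.
- Protocol, Method, logistics: "Wrist monitors can be mailed to and from patients using prepaid envelopes".
- Protocol, Examinations: exam two is 1-3 days and exam three 14-21 days after second-eye surgery. No exam lists issuing, fitting or collecting a monitor.

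**The concern.** The Objective says when activity is to be measured. The Method says for how long, but not from which day. A patient handed or mailed a monitor for use after surgery would most naturally put it on at once. Ten days from then end early in week two, and most of the recording belongs to week one.

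Two things are at stake. If all worn days are averaged, the result reported as week two is mostly something else. If only week-two days are used, the primary value rests on a few days. With no stated start, patients may also begin on different days, so the measured window could differ between patients.

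An analysis plan can choose among recorded days and define valid ones. It cannot recover days on which no monitor was worn, so the start of wear has to be settled in the instructions for data collection.

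**Working it through.** The protocol gives no overlap figure to reproduce, so this is a day count.

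**Inputs.** Wear lasts 10 days (Method). The endpoint is week two (Objective). The eyes are 7 to 14 days apart (Method). Assumptions: day 0 is second-eye surgery, and week two is days 8-14 or, with the other common numbering, days 7-13.

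**Formula.** For start day s and week two running from day a to day b, overlap = max(0, min(s+9, b) − max(s, a) + 1).

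| Start day | Days worn | Overlap with days 8-14 | Overlap with days 7-13 |
|---|---|---|---|
| 0 | 0-9 | 2 | 3 |
| 1 | 1-10 | 3 | 4 |
| 2 | 2-11 | 4 | 5 |
| 3 | 3-12 | 5 | 6 |
| 4 | 4-13 | 6 | 7 |
| 5 | 5-14 | 7 | 7 |
| 6 | 6-15 | 7 | 7 |
| 7 | 7-16 | 7 | 7 |
| 8 | 8-17 | 7 | 6 |

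**Immediate start (day 0 or 1).** Overlap is 2-4 days. So 7 − 4 = 3 to 7 − 2 = 5 days of week two go unrecorded, and 6-8 of the 10 worn days lie in week one or on the day of surgery.

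**Other readings.**
- Start at exam two (days 1-3): 3-5 days (week two = 8-14) or 4-6 days (7-13), together 3-6.
- Week two counted from the first eye, with wear starting on day 0 or 1 after the second: 6-7 days if the eyes are 7 days apart, 0-1 if they are 14 days apart.
- Week two taken as days 14-20, immediate start: 0 days.
- Full coverage: a start on days 5-8 (week two = 8-14) or 4-7 (7-13). Days 5-7 serve both.

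**Dilution if all 10 days are averaged.** With k week-two days and a week-one gain equal to a fraction f of the week-two gain, the average shows k/10 + (1 − k/10)f of the week-two gain. For k = 3: 30% at f = 0, 65% at f = 0.5, 100% at f = 1. For k = 2 and k = 4: 20% and 40% at f = 0, 60% and 70% at f = 0.5. The value of f is assumed; the protocol says nothing about it.

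**Precision if only week-two days are used.** Let t be the between-patient variance of change divided by the one-day variance, with days independent. Against a 10-day baseline, the variance relative to a fully recorded week two is (1/k + 1/10 + t)/(1/7 + 1/10 + t).
- t = 0: 1.44 (k = 4), 1.78 (k = 3), 2.47 (k = 2).
- t = 0.5: 1.14, 1.26, 1.48.

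The value of t is also assumed.

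**Alignment with controls.** Assume the surgery group's baseline ends at first-eye surgery and the controls' interval runs from the end of their baseline. Controls then restart after 14 days. A start on days 5-7 after the second eye falls 7 + 5 = 12 to 14 + 7 = 21 days after first-eye surgery. An immediate start falls 7 + 0 = 7 to 14 + 1 = 15 days after it.

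**The case against.** The strongest reply is that the text contains no contradiction. Wear after surgery need not begin immediately, and ten days that include week two satisfy both sentences. Mailing frees the start from any visit. That stands: the defect is a missing start day and a missing anchor, and the 2-4 day figure is conditional on an immediate start after the second eye.

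It may also be said that week two loosely means the first two weeks. Wear on days 1-10 would then lie wholly inside days 1-14, with 4 of those 14 days unrecorded. The text does not say so.

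A reader might go further and infer that the Method as written misses its endpoint, that the effect will be diluted to 30%, or that the variance will rise 1.8-fold. The documents support none of these. No immediate start is directed. The 30% needs no gain at all in week one. The 1.8 needs independent days and no variation between patients in their change; at t = 0.5 it is already down to 1.26.

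Finally, this is a 30-patient pilot with no stated power target. That lowers the severity, but a pilot's primary result still has to describe the period it names.

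**Conclusion.** The point holds as an unreconciled specification. The primary endpoint names week two, and the surgery group's wear instruction fixes neither the start day nor the eye from which days are counted.

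On the natural reading, 2-4 of the 10 worn days fall in week two and 3-5 of its 7 days are lost for good. Across the readings that the text allows, the overlap runs from 0 to 7 days. These counts rest only on the day numbering, the start day and the anchoring eye.

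No size of bias or loss of precision can be established, because f and t are not in the protocol; the figures above show a range and are not estimates. The text should be corrected before second wear periods begin. The documents do not show that the primary result is already compromised.

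**What to change.** Make the Objective and the Method name the same days, counted from second-eye surgery, by one of two routes:

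- **(a)** State a monitor start day that covers week two (day 5, 6 or 7 works under either numbering), and define the primary post-operative value as the mean per day over the week-two days, compared with the baseline mean per day.
- **(b)** Keep immediate wear and rename the endpoint to the days actually worn, for example post-operative days 1-10.

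Under either route, state how the timing lines up with the control group's second wear after its 14-day interval.

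The cost is a short clarification of the text and, under (a), a later start for the monitor. No visit is added: monitors may already be mailed, and exam three ("Post-operative exam three, 14-21 days after cataract surgery second eye") can follow the last wear day, which would be day 14, 15 or 16. Under (a) the first 4-6 post-operative days go unrecorded and the monitor comes back later. Under (b) the endpoint is mostly a week-one measure and must be reported as one. The change concerns monitor timing only and leaves patient care as it is.
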